8.4 AE Reporting

All AEs, regardless of severity and whether or not they occurred during the treatment or follow-up period, are to be recorded on the appropriate AE pages in the CRF. The investigator will include the date of onset and duration of the AE, as well as the severity and causality of each AE, and the actions taken. Each event should be recorded separately.

The investigator shall report all AEs and SAEs into the e-CRF, without reporting to Istituto di Ricerche Farmacologiche Mario Negri IRCCS.

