3.1 Participating centers

The Promoter of the study is the Istituto di Ricerche Farmacologiche Mario Negri IRCCS.

The coordinating center for patients' enrolment is the ASST Monza Ospedale San Gerardo.

Satellite centers placed in the entire national territory will be involved in the study.

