8.3 Causality

The causal relationship between the study drug and the AE will be characterized as unrelated, unlikely, possible, probable or unknown (unable to judge). Events can be classified as “unrelated” if there is not a reasonable possibility that the study medication caused the AE.

- An “unlikely” relationship suggests that only a remote connection exists between the study drug and the reported AE. Other conditions, including chronic illness, progression, or expression of the disease state or reaction to concomitant medication, appear to explain the reported AE.
- A “possible” relationship suggests that the association of the AE with the study medication is unknown; however, the AE is not reasonably supported by other conditions.
- A “probable” relationship suggests that a reasonable temporal sequence of the AE with drug administration exists and, in the Investigator’s clinical judgment, it is likely that a causal relationship exists between the drug administration and the AE, and other conditions (concurrent illness, progression or expression of disease state or concomitant medication reactions) do not appear to explain the AE.

All efforts should be made to classify the AE according to the above categories. The category “unknown” (unable to judge) may be used only if the causality is not assessable, e.g. because of insufficient evidence, conflicting evidence, conflicting data, or poor documentation.

The assessment of whether there is a reasonable possibility of a causal relationship is made by the investigator. In the absence of information on causality from the reporting investigator, the Istituto di Ricerche Farmacologiche Mario Negri IRCCS should consult the reporting investigator and encourage him/her to express an opinion on this aspect. The causality assessment given by the investigator should not be downgraded by the Istituto di Ricerche Farmacologiche Mario Negri IRCCS. If the Istituto di Ricerche Farmacologiche Mario Negri IRCCS disagrees with the investigator's causality assessment, the opinion of both the investigator and the Istituto di Ricerche Farmacologiche Mario Negri IRCCS should be provided with the report.

For more detail about seriousness criteria, refer to "Common Terminology Criteria for Adverse Events (CTCAE)" Version 5.0 Published: Nov 27, 2017 from the U.S. DEPARTMENT OF HEALTH AND HUMAN SERVICES National Institutes of Health National Cancer Institute.

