8.5 Reporting of SAEs and SUSARs

Any SAEs will be reported immediately to Istituto di Ricerche Farmacologiche Mario Negri IRCCS pharmacovigilance representative within 24 hours of the investigator becoming aware of the event. The SAE form, along with any additional information necessary in evaluating the SAE (such as laboratory reports or hospital notes), should be included. The Istituto di Ricerche Farmacologiche Mario Negri IRCCS will keep detailed records of all AEs related to the study that are reported by the investigator.

The immediate report shall be followed by detailed, written reports. The immediate and follow-up reports shall identify subjects by their unique code numbers.

The Medicines for Human Use (Clinical Trials) Regulations 2004 (Statutory Instrument 1031) and subsequent amendments define the following terms:

A suspected unexpected serious adverse reaction (SUSAR) that is fatal or life-threatening must be

reported to the competent authority and ethics committee within 7 days after the Istituto di Ricerche Farmacologiche Mario Negri IRCCS became aware of the event. Any additional information must be reported within 8 days of sending the first report.

A SUSAR that is not fatal or life-threatening must be reported to the competent authority and ethics committee as soon as possible (within 15 days) after the Istituto di Ricerche Farmacologiche Mario Negri IRCCS becomes aware of the event.

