10.3 Database management and quality control

A web-based Clinical Data Management System (CDMS/eCRF), named FEATHER, is provided by Istituto di Ricerche Farmacologiche Mario Negri IRCCS to capture and verify study data.

Each eCRF user will be authorized to access to the application only through a protected computer (client) and providing personal credentials to login.

eCRF manager/administrator organizes users in different roles groups (es. project manager, data manager, clinical monitor, study investigators). Some groups will be able to edit and store patient's data and other groups will validate and lock the inserted data.

Every enabled user would be authorized to view/edit only data necessary to complete his task. Locked data can't be modified.

eCRF activity is automatically logged and data editing is stored in a digital audit trail. eCRF captured data is stored and protected in high-security network.

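### Sections 8.4 and 8.5 give opposite instructions on reporting SAEs to the promoter, so a site can miss the 24-hour report and the SUSAR periods can start late

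*Combined protocol and SAP*

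**What the plan says.** Section 8.4 covers the recording of adverse events on the AE pages of the CRF. It closes with an instruction that names serious events explicitly: "The investigator shall report all AEs and SAEs into the e-CRF, without reporting to Istituto di Ricerche Farmacologiche Mario Negri IRCCS".

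Section 8.5, which deals with SAEs and SUSARs, sets a different rule: "Any SAEs will be reported immediately to Istituto di Ricerche Farmacologiche Mario Negri IRCCS pharmacovigilance representative within 24 hours of the investigator becoming aware". It also asks for an SAE form, any supporting documents needed to evaluate the event, and detailed written follow-up reports.

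Section 3.1 settles who the recipient is: "The Promoter of the study is the Istituto di Ricerche Farmacologiche Mario Negri IRCCS".

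The onward deadlines in 8.5 are tied to that institute's knowledge. A fatal or life-threatening SUSAR must be "reported to the competent authority and ethics committee within 7 days after the Istituto di Ricerche Farmacologiche Mario Negri IRCCS became aware" of it. Any other SUSAR must be reported as soon as possible, "within 15 days) after the Istituto di Ricerche Farmacologiche Mario Negri IRCCS becomes aware of the event".

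Section 8.3 gives the promoter a part in assessing causality: "In the absence of information on causality from the reporting investigator, the Istituto di Ricerche Farmacologiche Mario Negri IRCCS should consult the reporting investigator". If the promoter disagrees with the investigator's assessment, both opinions go with the report.

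**The concern.** The two sections address the same actor (the investigator), the same events (SAEs) and the same recipient (the promoter). One waives the report and the other demands it within 24 hours. Under section 11.2 the investigator signs to follow all of the protocol's instructions, which is impossible here. In a multicenter trial, different sites may resolve the conflict in different ways.

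What is at stake is the timeliness of expedited safety reporting. The SUSAR periods start from the promoter's awareness, so a missing site report does not show up as a missed SUSAR deadline. It moves the start of the period instead. A promoter could meet the 7-day or 15-day limit on paper although the event had been known at the site for much longer.

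**Working it through.** The protocol gives no derived figure to reproduce here. The check compares the sections and then looks at what the deadlines imply.

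**Step 1: do the sections really conflict?**

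| | Section 8.4 | Section 8.5 |
|---|---|---|
| Who acts | Investigator | Investigator |
| Events | All AEs and SAEs | Any SAE |
| Where the event goes | e-CRF | Promoter's pharmacovigilance representative |
| Report to promoter | Excluded | Required |
| Time limit | None stated | 24 hours from investigator awareness |
| Documents | AE pages of the CRF | SAE form, supporting records, written follow-up |

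Because 8.4 names SAEs, it cannot be read as covering non-serious events only. If it means merely that no separate report is needed beyond the e-CRF, it still contradicts 8.5, which requires one.

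**Step 2: does the protocol say which rule prevails?** No section does so. The context favors 8.5: it is the dedicated SAE section with a full procedure, and the promoter's causality role in 8.3 presupposes that the event has reached it. That shows which sentence is out of place, but it is not a precedence rule that a site could apply.

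**Step 3: can the e-CRF replace the report?** Section 10.3 says that the data system, "named FEATHER, is provided by Istituto di Ricerche Farmacologiche Mario Negri IRCCS to capture and verify study data". Section 10.2 makes CRFs accessible to the promoter, and section 10.1 provides for on-site and, where needed, remote monitoring. None of these sections describes an automatic SAE alert, a deadline for entering an SAE, or a monitoring frequency. The e-CRF is therefore a possible route to awareness, with no stated time limit.

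**Step 4: what happens to the SUSAR periods?** Let D be the number of days from the investigator's awareness to the promoter's awareness. Assume that the promoter is aware when the report arrives or when it sees the e-CRF entry.

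- Latest SUSAR submission after investigator awareness, fatal or life-threatening: D + 7 days.
- Latest SUSAR submission after investigator awareness, other: D + 15 days.
- Under 8.5, D is at most 1, so the limits are 1 + 7 = 8 days and 1 + 15 = 16 days.
- Under 8.4, D is the time until the promoter sees the e-CRF entry. The protocol puts no upper bound on it. Where D exceeds 1, each limit is exceeded by D − 1 days.

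If the promoter sees an entry within a day, the awareness date is not delayed, although the SAE form and supporting documents would still be missing. If the entry waits for the next data review or monitoring visit, the delay is as long as that wait.

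**The case against.** The best defense is that 8.4 is a drafting slip that no careful site would act on. Its heading concerns AEs and most of its text is about which fields to complete. Section 8.5 is headed for SAEs and SUSARs and gives a complete procedure. Section 8.2 refers investigators to GCP and national legislation on how and when to refer to AEs, SAEs and SUSARs, and section 11.1 binds the trial to ICH GCP and local regulations. The drugs are marketed and are to be used according to their product summaries. Nothing about the sample size, margin, endpoint or analysis is touched.

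Much of this stands. 8.5 is very probably the intended rule, and many sites would follow it. But a pointer to outside rules does not reconcile two conflicting instructions inside the protocol, and 8.4 addresses SAEs by name.

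The defense also rightly limits the consequences. A reader might infer that a site following 8.4 would never start the SUSAR clock. The documents do not support that: the SAE is still entered in a system that the promoter provides and can access, so awareness may come late but is not ruled out. A reader might also infer that the DMC would work from incomplete SAE data. That is not shown either. Section 8.4 itself requires every SAE to be in the e-CRF, and section 8.7 lets the DMC review study information at patient or group level, with meetings tied to enrollment of at least 25% and then 50%. It does not say that the DMC relies on the 24-hour reports.

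**Conclusion.** This is an internal contradiction, wrong as written, and it must be fixed because it concerns expedited safety reporting. The supported consequence is delay. A site that follows 8.4 sends no 24-hour report and no SAE form, and the 7-day and 15-day SUSAR periods may start late by an amount that the protocol leaves unbounded.

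Every SAE at a site that follows 8.4 is exposed. How many that would be cannot be stated, because the documents give neither an expected SAE count nor any indication of how sites read the two sections. The conclusion rests on the wording of 8.4 and 8.5 and on the absence of a precedence rule, an SAE alert or an entry deadline. If such an arrangement exists in a manual outside these documents, the practical risk is smaller, but the protocol text still contradicts itself.

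**What to change.** Reconcile 8.4 with 8.5. In 8.4, limit the exemption from reporting to the promoter to non-serious AEs. Then add a sentence such as: All SAEs are entered in the e-CRF and are also reported to the promoter within 24 hours, as described in section 8.5. Nothing in 8.5 needs to change.

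The cost is a short wording change made through a written amendment, which under section 11.4 needs approval by each participating institution's ethics committee. It adds no work for sites beyond what 8.5 already requires.

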8.5 Reporting of SAEs and SUSARs

Any SAEs will be reported immediately to Istituto di Ricerche Farmacologiche Mario Negri IRCCS pharmacovigilance representative within 24 hours of the investigator becoming aware of the event. The SAE form, along with any additional information necessary in evaluating the SAE (such as laboratory reports or hospital notes), should be included. The Istituto di Ricerche Farmacologiche Mario Negri IRCCS will keep detailed records of all AEs related to the study that are reported by the investigator.

The immediate report shall be followed by detailed, written reports. The immediate and follow-up reports shall identify subjects by their unique code numbers.

The Medicines for Human Use (Clinical Trials) Regulations 2004 (Statutory Instrument 1031) and subsequent amendments define the following terms:

A suspected unexpected serious adverse reaction (SUSAR) that is fatal or life-threatening must be

reported to the competent authority and ethics committee within 7 days after the Istituto di Ricerche Farmacologiche Mario Negri IRCCS became aware of the event. Any additional information must be reported within 8 days of sending the first report.

A SUSAR that is not fatal or life-threatening must be reported to the competent authority and ethics committee as soon as possible (within 15 days) after the Istituto di Ricerche Farmacologiche Mario Negri IRCCS becomes aware of the event.

8.6 Follow up of AE/SAE/DAR/DAE/SUSAR

Any AE/SAE/DAR/DAE/SUSAR observed from screening/randomization up to the end of the study will be followed up to resolution. Resolution means that the subject has returned to a baseline state of health or the Investigator does not expect any further improvement or worsening of the AE.

8.7 Data Monitoring Committee (DMC)

According to the EMEA GUIDELINE ON DATA MONITORING COMMITTEES (January 2006) a Data Monitoring Committee (DMC) is an external group of independent experts assessing the progress, safety data and efficacy endpoints of this clinical study. In order to do so, a DMC may review study information (on a patient level or treatment group level) during the conduct of the study. Based on its review, the DMC provides the Principal Investigator with recommendations regarding study modification, continuation or termination. Safety monitoring will be the major task for a DMC. The DMC might need access to efficacy information to perform a risk/benefit assessment in order to weigh possible safety disadvantages against a possible gain in efficacy.

Based on the results of the monitoring activities, the DMC is expected to consider recommendations about stopping the trial for efficacy and/or safety and/or for sample size adjustment without violating the concepts behind the original study protocol.

If changes in the study conduct are recommended by a DMC, sufficient information should be provided to allow the Principal Investigator to decide whether and how to implement these recommendations. The implementation of any DMC recommendation is solely the responsibility of the Principal Investigator who is also free to neglect (in whole or in part) recommendations of a DMC.

The DMC has to be fully functional before enrolment into the study starts to enable it to respond to any safety signal.

As DMC work is a multidisciplinary task, the DMC needs expertise from different scientific areas. The member of the DMC will include a biostatistician, a member of an ethical committee, a neurologist and a pharmacovigilance expert.

All members of the DMC will be qualified persons, they should also have practical experience with conducting clinical trials, a good understanding of the problems and limitations of clinical trials, have no financial interest in the outcome of the study.

The DMC will meet after the enrollment of at least 25% of patients and after three months of study.

The following DMC meeting will take place after the enrollment of 50% of patients.

9. Resource utilization

The study foresees a charge for the hosting institutions. The randomization (Visit 1) and follow-up visits as well as drug delivery will be performed by local investigators who have completed adequate training and are listed in the signature log. This trial is an independent investigation according to the Ministry Decree (DM) # 43 dated December 17 2004. In keeping with the Italian law, the trial will receive an insurance coverage (DM 213, July 14 2009). Laboratory tests will be performed by the local laboratory and prescribed as part of the routine evaluation.

10 Data review and management

10.1 Site monitoring

On site monitoring will be performed in order to review the -CRFs for completeness and accuracy and will instruct site personnel to make any required corrections or additions. Where needed, remote monitoring will be performed.

10.2 Data collection

All trial demographic and clinical data will be collected by the designated investigators at each scheduled visit. The CRFs are made accessible to the Istituto di Ricerche Farmacologiche Mario Negri IRCCS or by the study site investigators, one copy being retained at the study site.

10.3 Database management and quality control

A web-based Clinical Data Management System (CDMS/eCRF), named FEATHER, is provided by Istituto di Ricerche Farmacologiche Mario Negri IRCCS to capture and verify study data.

Each eCRF user will be authorized to access to the application only through a protected computer (client) and providing personal credentials to login.

eCRF manager/administrator organizes users in different roles groups (es. project manager, data manager, clinical monitor, study investigators). Some groups will be able to edit and store patient's data and other groups will validate and lock the inserted data.

Every enabled user would be authorized to view/edit only data necessary to complete his task. Locked data can't be modified.

eCRF activity is automatically logged and data editing is stored in a digital audit trail. eCRF captured data is stored and protected in high-security network.

10.4 Outcome measures, statistical methods and data analysis

Expected outcomes are the following:

1. compared to patients assigned to standard daily doses, patients receiving low daily doses of AEDs are expected to incur in similar rates of seizure recurrence;
2. compared to patients assigned to standard daily doses, patients receiving low daily doses of AEDs are expected to undergo significantly less treatment changes due to intolerable drug-related adverse events;
3. compared to patients assigned to standard daily doses, patients receiving low daily doses of AEDs are expected to experience less drug-related intolerable adverse events;
4. compared to patients assigned to standard daily doses, patients receiving low daily doses of AEDs are expected to experience a better quality of life;
5. the National Health System is expected to incur in significant savings with low daily doses of AEDs.

Primary outcome

The proportion of patients experiencing a treatment failure motivated by the need to change the assigned dose or the assigned drug for seizure relapse during the follow-up.

Secondary outcomes

1. the proportion of patients experiencing a treatment failure motivated by intolerable drug-related adverse events during the follow-up;
2. QOLIE-31 total score at the last visit;
3. the score of the seven PSQ-18 subscales (general satisfaction, technical quality, interpersonal manner, communication, financial aspects, time spent with doctor, accessibility and convenience) at the last visit;
4. the mean daily patient's cost of health care resources consumed for the management of epilepsy during the first 12 months of the study.

Descriptive statistics will be provided for all the data collected at admission, comparing the two

treatment regimens. Numerical variables will be described using means, standard deviations, medians and ranges, while categorical variables using frequencies and percentages. The proportion of patients experiencing the primary end-point over the entire follow-up will be estimated using Kaplan-Meier survival curves. The difference between the two treatment arms in the proportion of patients experiencing the primary endpoint, with 95% confidence intervals (95% CI), will be calculated at 1, 3, 6, 9 and 12 months, and compared to the non-inferiority margin (m). In presence of variables at admission having a different distribution in the two treatment groups and that could have an effect on treatment response (possible confounders), a multivariable analysis will be also performed using a Cox's proportional hazards model, adjusted for these variables. A hazard ratio (HR), with the corresponding 95% CI, will be reported, and compared to a relative risk (RR) obtained considering as reference the proportion of patients experiencing the primary endpoint in the standard dose arm (p_0) and taking into account the non-inferiority margin ($RR=(p_0+m)/p_0$). The secondary end-point will be evaluated using Kaplan-Meier survival curves, comparing the two treatment arms with the log-rank test. In presence of possible confounders with a different distribution in the two treatment arms at baseline, a Cox's proportional hazards model will be used. The QOLIE-31 total score, the seven PSQ-18 subscales scores at the last visit, and mean daily patient's costs will be compared, separately, between treatment arms using the t-test, the Wilcoxon-Mann-Whitney test, or a multivariable linear regression model. Subgroup analyses will be performed separately for sex, age groups, drug, seizure types (focal/focal-to-bilateral), etiology (known/unknown), and center.

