3.5 Data collection at baseline and during follow-up

The following variables will be collected at admission by the evaluating physician: date of birth, sex, height, weight, arterial blood pressure, heart rate, family history of epilepsy, history of febrile seizures, date of onset of seizures, seizure type(s), epilepsy syndrome or non-syndromic epilepsy, neurological and psychiatric examination (coded as normal or abnormal), first interictal EEG (coded as normal, slow or epileptiform), imaging findings (coded as normal or abnormal for seizure etiology), relevant comorbidities, concurrent treatments, HRQOL (using the Italian version of the QOLIE-31 inventory; Beghi et al, 2005), patient satisfaction (PSQ-18), laboratory examinations if available (CBC, alanine aminotransferase, aspartate aminotransferase, gamma glutamyltranspeptidase, creatinine, alkaline phosphatase, calcium, phosphorus, sodium, potassium, ammonia, amylase). Each patient will be followed for 12 months. In the follow-up visits the same laboratory tests will be performed as per clinical practice or caring physician discretion, including the AED plasma concentration assay. Ad-hoc diaries will be given to each patient and/or caregiver for the collection of follow-up data. The diaries will include the number of seizures (with dates) and the type and severity of adverse events (with dates, outcome and actions). To preserve blindness, daily intake and timing of the assigned, but not the daily dose, will be recorded in the diaries. Any contact with the National Health System for the management of seizures and AEDs will be also noted in the diaries with dates. The contents of the diaries will be verified during each telephone contact by the evaluating physician and by the treating physician at the time of the face-to-face visits.

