6.4 Treatment blinding

The study is single-blind. Only the evaluating physician will be blinded to the assigned treatment schedule.

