Follow-up visits will be scheduled at the discretion of the caring physician but telephone contacts will be programmed at 4 weeks, 3, 6, 9 and an on-site clinic visit at 12 months. An interval of ± 1 week for the visit schedule is permitted. During each contact the patient will be asked to report any seizure recurrence, adverse event and any additional information deemed important for the management of the disease. Patients will be invited to read the diaries and verify if any missing or incomplete information was present.

The following evaluations will be performed during site visits:

1. Evaluation of possible relapses, compliance with treatment schedule and adverse events;
2. Recording of clinical parameters: weight, arterial blood pressure, heart rate;
3. Neurological examination;
4. General clinical history: concomitant diseases and medications;
5. Recording of the plasma concentration of the assigned drug and laboratory examinations previously specified (only if required as per clinical practice);
6. Administration of the QOLIE-31 and PSQ-18 inventories (only at 12 months);
7. Report of a standard, interictal EEG if performed as per clinical practice;
8. Report of the daily intake of assigned drug and timing of the assigned dose;
9. Report of all the contacts with the National Health System (NHS) for the management of seizures and AEDs;
10. Receipt of the seizure diary, control for quality and completeness, and delivery of a new diary.

The diaries will be examined by an investigator different from the treating physician (the evaluating physician) who will be blinded to the assigned drug schedule

The following evaluations will be performed during phone contacts:

1. Evaluation of possible relapses, compliance with treatment schedule and adverse events;
2. General clinical history: concomitant diseases and medications;
3. Report of the daily intake and timing of the assigned dose;
4. Report of a standard, interictal EEG, if performed;
5. Recording of the plasma concentration of the assigned drug and laboratory examinations previously specified, if performed;
6. Report of all the contacts with the NHS for the management of seizures and AEDs.

In case of seizure relapse or treatment change due to adverse events, the patient will exit the study and antiepileptic treatment will be modified if required by the treating physician.

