8.2 Severity

The severity of the AE will be characterized as “mild, moderate or severe” according to the following definitions:

- Mild events are usually transient and do not interfere with the subject’s daily activities.
- Moderate events introduce a low level of inconvenience or concern to the subject and may interfere with daily activities.
- Severe events interrupt the subject’s usual daily activity.

Seriousness: The judgment as to whether the event is serious is usually made by the reporting investigator who must conform to the standard definition.

The physician will assess the seriousness, intensity, and causality of each AE, and the actions taken, including the discontinuation of the experimental drug, where required by the site investigator or the patient (Refer to GCP/1997 and to D.L N 211/2003 for explanation about how and when to refer to AE, SAE, SUSAR, DAR and their definitions).

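### Every treatment change for an adverse event ends participation, but only changes labelled intolerable and drug-related count as tolerability failures, and the plan neither defines that label nor requires a blinded assessor to give it

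*Combined protocol and SAP*

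**What the plan says.** **Endpoint.** Section 2.4 lists treatment failure from intolerable drug-related adverse events as the first secondary endpoint. Section 10.4 restates it as "the proportion of patients experiencing a treatment failure motivated by intolerable drug-related adverse events during the follow-up". Section 2.2 sets the aim of showing that the proportion is lower on the low dose, and 10.4 tests it with Kaplan-Meier curves and a log-rank test.

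**Exit rule.** Section 7.2 has no such qualifier: "In case of seizure relapse or treatment change due to adverse events, the patient will exit the study".

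**Scales.** Section 8.2 grades severity as mild, moderate or severe. Section 8.3 has five causality categories: unrelated, unlikely, possible, probable and unknown.

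**Who judges.** Section 8.2: "The physician will assess the seriousness, intensity, and causality of each AE, and the actions taken". Section 8.3: "The assessment of whether there is a reasonable possibility of a causal relationship is made by the investigator". Neither says whether this is the treating or the evaluating physician.

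**Who is blinded.** Section 6.4: "Only the evaluating physician will be blinded to the assigned treatment schedule". The evaluating physician does take part in adverse-event review. Section 7.2 states: "The diaries will be examined by an investigator different from the treating physician (the evaluating physician) who will be blinded". Under 3.5 the diaries, which hold the type and severity of adverse events, are "verified during each telephone contact by the evaluating physician and by the treating physician at the time of the face-to-face visits".

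**The concern.** A patient whose treatment is changed for an adverse event leaves the study whatever label is attached. The label then decides whether that exit is a tolerability failure. Without it, the exit counts neither there nor in the primary endpoint, which concerns relapse only, and 10.4 does not say how such exits are handled.

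The label therefore sits inside the endpoint definition. Intolerable is not defined, and no rule says which causality categories make an event drug-related. Because the assessor is not named, someone who knows the dose may do the labelling in a trial whose stated hypothesis is that low doses cause fewer adverse effects. If the same complaint is called drug-related more readily on the standard dose, the low dose looks better tolerated with no real difference behind it. No blinded adjudication and no analysis of all adverse-event-driven changes is planned, so a reader of the results could not separate a real benefit from attribution.

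**Working it through.** **1. Exit rule against endpoint.**

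| Event | Leaves study (7.2) | Primary failure (2.3) | Tolerability failure (2.4, 10.4) |
|---|---|---|---|
| Dose or drug change for seizure relapse | yes | yes | no |
| Change for adverse event, labelled intolerable and drug-related | yes | no | yes |
| Change for adverse event, not so labelled | yes | no | no |

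The third row is the gap.

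**2. The plan's own figure.** The documents give no event rate, effect size or power for tolerability. The only sample size is for the primary endpoint (10.6): 60% seizure-free in both arms, absolute margin 15 points, one-sided 0.025, 80% power.

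n per arm = (1.960 + 0.842)² × 2 × 0.60 × 0.40 / 0.15² = 167.4, rounded up to 168. Total = 336 / 0.90 = 373.3, rounded up to 374. Both match the plan. With 1:1 allocation, 374 / 2 = 187 per arm, which is used below.

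**3. Effect of labelling alone, simple proportions.** Assume the same true rate r of adverse-event-driven change in both arms. Assume 90% of changes are labelled on standard and a share a on low.

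x = 0.90r; y = a·r; SE = √[x(1−x)/187 + y(1−y)/187]; chance of a significant result favouring low = Φ((x−y)/SE − 1.96).

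Example, r = 20%, a = 60%: x = 0.18, y = 0.12, SE = 0.0368, so Φ(1.63 − 1.96) = 0.37. The apparent benefit is 6 points and the apparent risk ratio is 0.12 / 0.18 = 0.67.

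| r | 90% v 75% | 90% v 60% |
|---|---|---|
| 10% | 7.6% | 19.6% |
| 15% | 9.7% | 28.1% |
| 20% | 11.9% | 37.1% |

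**4. Closer to the planned test.** Step 3 overstates the effect, because relapse also removes patients and 10.4 specifies a log-rank test. The check was repeated by simulation: 187 per arm, exponential times, 40% relapse at 12 months in both arms (the complement of the 60% in 10.6), with relapses and unlabelled adverse-event exits censored. The censoring is an assumption, since 10.4 is silent.

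| Labelled, standard v low | Chance of a false low-dose benefit, r = 10 to 20% |
|---|---|
| Equal labelling | about 2.5% |
| 90% v 75% | about 6 to 9% |
| 90% v 60% | about 14 to 26% |

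Separate runs agree to within about a percentage point. A 10-point gap (90% v 80%) gives only 5 to 7% over these rates even by the simple-proportion formula, which errs high.

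**5. Counting every adverse-event-driven change.** In the same simulations the false-positive chance was 2.0 to 2.9% at every labelling gap tried, against 2.5% nominal. This follows from assuming equal true change rates. It shows that the labelling step is removed, not that the decision to change treatment is unbiased.

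**The case against.** **The labeller is not shown to know the arm.** A reader might infer from 6.4 that the label is given by an unblinded treating physician. The documents do not say so. Sections 8.2 and 8.3 name only the physician or the investigator; 7.2 calls the blinded evaluating physician an investigator; and that person examines the diaries and makes the telephone contacts. This objection stands. What remains is that the assessor is unspecified and blinded attribution is not required.

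**A treatment change is not a hard event either.** Section 8.2 refers to actions "including the discontinuation of the experimental drug, where required by the site investigator or the patient". Neither the treating physician nor the patient is blinded, and a complaint may prompt a change on one dose and observation on the other. This also stands. It is why the wider count is proposed beside the labelled endpoint and not as its replacement.

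**An exit rule may properly be wider than an endpoint.** True. The hypothesis concerns drug toxicity, and the endpoint agrees with the objective in 2.2. The difference is not a contradiction in itself. It matters here because the narrowing terms have no operational rule and the unlabelled exits have no stated handling.

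**The magnitude rests on assumptions.** It does. The documents neither give nor exclude a labelling gap, and a sizeable one is needed for a large effect.

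**Conclusion.** The point holds in a limited form. The exit rule is wider than the counted endpoint, both qualifying terms lack a rule, and nothing requires the blinded physician to assign the label. An apparent low-dose tolerability benefit could therefore arise partly from attribution.

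The size depends on a labelling gap of about 15 to 30 points, which takes the false-positive chance from 2.5% to somewhere between 6% and 26% under the step 4 assumptions. A reader might go further and conclude that the tolerability result is biased toward low dose. The documents do not support that: they establish an unprotected step, not a demonstrated bias.

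This concerns a secondary endpoint. The primary endpoint and the sample size of 374 are unaffected. It should be corrected because the remedy is cheap.

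**What to change.** In section 10.4:

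1. Prespecify an analysis of every change or stop of the assigned dose or drug due to any adverse event, whatever its causality or severity label, reported beside the intolerable drug-related endpoint.
2. Claim a tolerability benefit only if the two analyses agree in direction and broadly in size.
3. Report the causality and severity labels of all adverse-event exits by arm.
4. State which of the 8.3 categories count as drug-related, how intolerable relates to the 8.2 grades, and how adverse-event exits without the label are handled.
5. Name the existing blinded evaluating physician as the person who assigns the label for this endpoint.

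**Cost.** Items 1 to 4 need wording only: section 8 already has severity, causality and actions taken recorded for each adverse event. Item 5 needs adverse-event information to reach the evaluating physician without the dose, as 3.5 already arranges for the diaries. Unrelated adverse events will slightly dilute a true dose effect in the added analysis. The changes remove labelling bias only, because the decision to change treatment remains unblinded; the report should say so.
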